**Confidential**

The information provided in this document is strictly confidential and is intended solely for the guidance of the clinical investigation. Reproduction or disclosure of this document whether in part or in full to parties not associated with the clinical investigation, or its use for any other purpose, without the prior written consent of the Principal Investigator is not permitted.

Throughout this document, symbols indicating proprietary names (®, TM) are not displayed. Hence, the appearance of product names without these symbols does not imply that these names are not protected.

*Version 2 / Date 05/08/2020*

PROTOCOL SUMMARY	
Study Title	Carolinas Cardiogenic Shock Initiative
Study Design	This is a case series and prospective patient registry
Study Objectives	To determine if deferred or delayed implantation of Impella device based on shock severity index is non-inferior with respect to 1 month and 1 year mortality compared to standard clinical protocols that do not differentiate based on shock severity in adult patients following an initial diagnosis of acute myocardial infarction complicated by cardiogenic shock (AMICS).
Study Population	The registry will include all eligible subjects from approximately 5/1/2019 until 4/30/2024, at participating sites.
Study Procedures	Adult patients with a diagnosis of AMICS will have their clinically available data contribute to the project registry. Patients who meet criteria for inclusion into the registry will have their chart reviewed periodically for the purposes of the registry, for proof of survival at one month and one year post-admission. Social Security Death Index (SSDI) data will be used to determine mortality at one month and one year if unable to confirm using the electronic health record. Patient clinical data will be pulled from the medical record and entered or migrated into a database for comparison and analysis. All data collected for the study will originate in the medical record from clinically available information, from a national death database, or from other publically available data sources.

**LIST OF ABBREVIATIONS**

ABBREVIATION	DEFINITION
AMICS	Acute Myocardial Infarction complicated by Cardiogenic Shock
ANT	Anterior
CathPCI Registry	Catheterization and/or percutaneous coronary intervention registry
CS	Cardiogenic Shock
DUA	Data Use Agreement
DMP	Data Management Plan
eCRF	Electronic Case Report Form
ECMO	Extracorporeal Membrane Oxygenation
HFrEF	Heart Failure with reduced ejection fraction
HFpEF	Heart Failure with preserved ejection fraction
IABP	Intra-aortic balloon pump
ICU	Intensive Care Unit
INF	Inferior
LAT	Lateral
LBBB	Left bundle branch block
MCS	Mechanical Circulatory Support
MOP	Manual of Procedures
NCDR	National Cardiovascular Data Registry
PAPI	Pulmonary Artery Pulsatility Index
PCI	Percutaneous Coronary Intervention
PI	Principal Investigator
RHC	Right Heart Catheterization
STEMI	S-T elevation myocardial infarction
TIA	Transient Ischemic Attack
TTM	Therapeutic Temperature Management

## **1. OBJECTIVES**

### **1.1. Hypotheses**

A standardized clinical protocol that selects patients for MCS based on shock severity, will be non-inferior with respect to 1 month and 1 year mortality, compared to standard clinical protocols that do not differentiate based on shock severity in adult patients following an initial diagnosis of acute myocardial infarction complicated by cardiogenic shock (AMICS).

Those patients with shock that is not severe and do not have MCS, have a mortality rate that is similar or better than patients who have severe shock and receive MCS.

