### **3. RATIONALE**

Existing protocols in Europe and the United States vary widely based upon device selection and timing of support, a finding that is complicated by the limited data in a condition that is difficult to evaluate (Thiele et al., 2015; O'Neill et al., 2014; Diepen et al., 2017). Protocols in Europe suggest the deployment of MCS following revascularization, an approach which may underutilize a key pathway to better outcomes (O'Neill et al., 2014; Zeymar & Thiele, 2017; Brodie et al., 1999). In contrast, a significant concern for the National Cardiogenic Shock Protocol is that the existing

protocol may lead to Impella utilization in milder forms of shock when it may not be needed, resulting in potentially high artificial survival rates, unnecessarily expensive resource utilization, and life-threatening complications. Moreover, alternative devices, such as IABP or ECMO, may be more appropriate in specific clinical situations (small femoral anatomy, mitral regurgitation, RV failure, hypoxemia).

A recent American Heart Association Scientific Statement on the contemporary management of Cardiogenic Shock advocates for the development of regionalized systems of care and outlines future research priorities (Diepen et al., 2017). The statement notes that when, how, and which MCS device should be used remains unclear. Thus, outcomes of treatment in specialized cardiogenic shock centers which offer all treatment options, should be evaluated further.

The objective of the Carolinas Cardiogenic Shock Initiative will be to evaluate outcomes associated with utilization of MCS prior to PCI or delayed implementation in patients after reperfusion, based upon shock severity. An algorithm will be utilized which allows device variation based upon patient specific factors, employing a protocol driven approach to de-escalation in specialized shock centers with access to a variety of treatment options. Whether this can improve upon the protocol adopted by the National Cardiogenic Shock Initiative is unknown. However, the initiative addresses specific concerns that have arisen, leading to broad variation in the international approach to cardiogenic shock. A likely secondary benefit, is that a regionalized protocol should reduce center specific provider variation, allowing better outcome analysis and ability to execute specific protocol adjustments as a quality improvement initiative.

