Specifically, our goal is, first, to examine the degree to which a standardized clinical protocol that selects patients for MCS based on shock severity will be non-inferior with respect to mortality when compared with a standard clinical protocol that does not differentiate based on shock severity among adult patients following an initial diagnosis of AMICS. Second, our goal is to determine the degree to which mortality rates of patients with AMICS differ on MCS exposure.

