#### **4.4.2.2. Hypothesis 2.**

### *Approach*

To evaluate this hypothesis, we will conduct a prevalence analysis using a multilevel regression model to obtain site-level prevalence estimates of participant mortality using the

general equation:  $\text{logit}(p_{ij}) = X'\beta + \alpha_i$ , where  $x_{ij} = (x_{ij1} \dots x_{ijq})'$  is a vector of  $q$  covariates,  $\beta = (\beta_1 \dots \beta_q)'$  is a vector of fixed effects and  $\alpha_i$  is the random effect for site (Raudenbush & Bryk, 2002). The model will include demographic variables (e.g., race, gender, age, etc.), as well as site-level data and cross-level interactions. The prevalence estimates will be calculated from the predictors in the multilevel regression where:  $\hat{p}_{ijk} = e^{\text{predictor}} / 1 + e^{\text{predictor}}$ . A follow-up evaluation will determine site-level prevalence rates by factors such as MCS and risk status categories, with the formula:  $\hat{p}_{ijk} = \sum_j \frac{n_{ijkl}}{n_{ijk}} \hat{p}_{ijkl}$ , where  $\hat{p}_{ijk}$  is the estimated prevalence of mortality in site  $i$  of risk status  $j$  at time  $k$ ,  $n_{ijkl}$  is the number of participants in site  $i$  that are of MCS (or risk status type)  $j$ , at time  $k$  and belong to demographic group  $l$  (i.e., a particular age, gender, race group),  $n_{ijk}$  is the total population in site  $i$  of risk status type  $j$ , at time  $k$  and  $\hat{p}_{ijkl}$  is the estimated prevalence of patient mortality in site  $i$  that are of risk status type  $j$  at time  $k$  and belong to demographic group  $l$ . We will compare these rates using risk difference and rate ratios (Agresti, 2013).

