#### Expected results

We expect patients with shock that is not severe and do not receive MCS, have a mortality rate that is similar or better than patients who have severe shock and receive MCS.

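### Hypothesis 2 defines its groups by MCS actually received, so membership depends on the course after the treatment decision and the contrast is open to selection bias of uncertain net direction

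*Protocol*

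**What the plan says.** Section 1.1 describes the first group of the second hypothesis and its expected outcome in these words: "Those patients with shock that is not severe and do not have MCS, have a mortality rate that is similar or better". The comparator in the same sentence is worded "than patients who have severe shock and receive MCS". The expected results under Section 4.4.2.2 repeat the first group: "We expect patients with shock that is not severe and do not receive MCS, have a mortality rate that is similar or better", against the same comparator. Section 4.4.2 puts the second goal as being to "determine the degree to which mortality rates of patients with AMICS differ on MCS exposure". The approach under Section 4.4.2.2 plans "site-level prevalence rates by factors such as MCS and risk status categories", counted at each time point. It does not tie either factor to the first assessment or to the initial treatment plan, and it gives no rule for a device placed late.

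The strategy itself allows for late devices. The Study Objectives in the Protocol Summary are about deferring or delaying Impella according to a severity index. The Rationale (Section 3) says outcomes will be evaluated for "utilization of MCS prior to PCI or delayed implementation in patients after reperfusion, based upon shock severity".

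**The concern.** If the strategy includes late MCS, whether a patient ever had MCS is known only after the treatment decision has been made and its consequences have begun. A group of non-severe patients without MCS therefore leaves out those who were first managed without a device and later received one. A group of severe patients with MCS leaves out those who died before implantation or never received a device for another reason.

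This differs from the plain fact that severe patients are sicker. Even as pure description, the first group's rate is not the mortality of non-severe patients whose MCS was deferred, and the second group's rate is not the mortality of severe patients. This is one of only two stated hypotheses. It bears on the primary objective (Section 1.2), which is to learn which patients with AMICS gain most from MCS. A reader who takes the first rate as the result of deferral would be working from a selected subset.

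**Working it through.** **The plan's own figure.** Only Hypothesis 1 has one. Section 4.4.2.1 gives 39.7% for control, 41.3% (taken here as the non-inferiority bound), 31% as the actual treatment rate, one-sided alpha 0.025, 80% power and an unpooled Z test. With equal groups:

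n per group = (1.960 + 0.842)² × (0.397 × 0.603 + 0.31 × 0.69) / (0.413 − 0.31)² = 7.849 × 0.4533 / 0.010609 ≈ 335.4, rounded up to 336.

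The total is 672, as stated, and power at 336 per group is 80.07%. That calculation compares protocol with protocol. It does not use the Hypothesis 2 groups, so nothing below affects it.

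**Step 1. Where each patient falls under the wording of Hypothesis 2.**

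| First severity | Later course | Hypothesis 2 group |
|---|---|---|
| Not severe | Never has a device (survives or dies) | First group |
| Not severe | Receives a device later | Neither |
| Severe | Receives a device | Comparator |
| Severe | Dies before a device, or never has one | Neither |

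**Step 2. Effect on the non-severe rate.** Take non-severe patients whose MCS was initially deferred. Let f be the share who later receive a device, p1 their mortality, and p0 the mortality of those who never do.

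- All deferred: (1 − f) × p0 + f × p1
- Group named in Hypothesis 2: p0
- Understatement: f × (p1 − p0)

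**Step 3. Range.** The protocol gives none of f, p0 and p1. I assume f of 5–30%, p0 of 20% or 30%, and p1 of 40–60%. The last range is borrowed from the overall AMICS mortality in Section 2. Understatement in percentage points:

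| f | p0 = 20%, p1 = 40–60% | p0 = 30%, p1 = 40–60% |
|---|---|---|
| 5% | 1.0–2.0 | 0.5–1.5 |
| 10% | 2.0–4.0 | 1.0–3.0 |
| 20% | 4.0–8.0 | 2.0–6.0 |
| 30% | 6.0–12.0 | 3.0–9.0 |

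The extremes are 0.05 × (0.40 − 0.30) = 0.5 points and 0.30 × (0.60 − 0.20) = 12 points. If p1 were 15%, the sign would reverse, from 0.05 × (0.15 − 0.20) = −0.25 points to 0.30 × (0.15 − 0.30) = −4.5 points.

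**Step 4. Non-severe patients who die before a device can be placed.** These stay in the first group and raise its rate. Suppose a share d deteriorates, a fraction g of those reach a device with mortality p1, the rest of them die without one, and stable patients have 15% mortality.

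- Named group: [(1 − d) × 0.15 + d × (1 − g)] / [(1 − d) + d × (1 − g)]
- All deferred: (1 − d) × 0.15 + d × (1 − g) + d × g × p1

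For example, d = 20%, g = 50% and p1 = 60% give 0.22/0.90 = 24.4% against 28.0%, a gap of 3.6 points. Over d of 10–30%, g of 30–80% and p1 of 40–60%, the understatement is 0.5 to 9.2 points. At p1 = 15% it again reverses.

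**Step 5. The comparator.** Let h be the share of severe patients who never receive a device, q0 their mortality, and q1 the mortality of those who do. The named comparator shows q1, while all severe patients show (1 − h) × q1 + h × q0. The comparator is therefore too low by h × (q0 − q1). If all of those lost died first (q0 = 1), this is h × (1 − q1). With q1 assumed at 40–60%, that is 0.4 to 0.6 points for each percentage point of h. In Step 3, each percentage point of f moves the first group by p1 − p0, which is 0.1 to 0.4 points. Which effect is larger depends on f and h, and the protocol gives neither.

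**The case against.** The strongest reply is that Hypothesis 2 carries no claim about deferral. The deferral strategy is tested by Hypothesis 1, with a protocol-versus-protocol contrast, a margin and a power calculation. Hypothesis 2 has no margin and no power calculation, and it never speaks of a deferred group. The rate it describes is correct for the patients it names. This stands as far as purpose goes. A reader might infer that Hypothesis 2 is there to prove that withholding early MCS is safe, but no section says so. It does not remove the dependence of both groups on the later course.

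A reader might also infer that patients who worsen are re-graded as severe and moved into the comparator, raising its mortality. No section describes re-grading. It would raise that rate only if those patients died more often than the severe group, for which there is no figure. Appendix A, which holds the algorithm, is not shown, so the circumstances of late implantation cannot be checked. Late MCS may be planned timing rather than rescue.

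Finally, Section 4.4.2.2 could accommodate a tabulated cell of non-severe patients with MCS, and the coding of late devices could be left to an analysis plan. The cell is possible, but the hypothesis does not use it. The group definition is also not left open: the protocol states it in the hypothesis and repeats it in the expected results.

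**Conclusion.** The defect in definition holds on the text. Both Hypothesis 2 groups are formed by treatment received within a strategy that includes delayed treatment, and no section shown anchors them to the decision point. The non-severe rate is understated by f × (p1 − p0), about 0.5 to 12 points under the assumed ranges. This requires that patients given delayed MCS die more often than those never given it, which is plausible where deferral has failed but is not documented.

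It is tempting to conclude that the bias favours the expected result. The documents do not support this, because losing severe patients who die before implantation lowers the comparator and works against it. The net direction is not established. Hypothesis 1 and the 672 patients are unaffected. The point should be fixed, but it does not undermine the main comparison.

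**What to change.** Define the Hypothesis 2 groups by severity class at first assessment and by initial strategy (MCS up front or deferred). Keep every patient in that group whatever device follows, and also if death comes before a device. Reword Section 1.1, and the expected results under Section 4.4.2.2, to match. Within the deferred group, report how many received delayed MCS and their mortality. Keep the as-treated contrast as supportive.

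The cost is one derived variable. Severity classification is already planned (Section 1.3), and procedure dates and times are already collected (Section 4.3). Where no device was ever placed, device times cannot show the initial strategy, so the derivation rule must say how it is assigned. The deferred group's rate may look less favourable. Clinical care is unchanged.

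Two limits remain. Undergoing PCI is an inclusion criterion (Section 4.2.1), so severe patients who die before PCI are outside the registry and regrouping cannot recover them. The regrouped contrast also still compares milder with sicker patients, so confounding by severity is not removed.

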### **1.2. Primary Objective**

The primary objective of this study is to contribute to the evidence base defining which types of patient with AMICS are likely to receive the most benefit from MCS.

### **1.3. Secondary Objectives**

Secondary objectives include:

- a. Develop and maintain a patient registry that includes electronic health record, administrative and patient reported outcomes data.
- b. Classify patients based on shock severity.

### **1.4. Exploratory Objective**

Further questions within the scope of the project may be examined using data within the registry, as a part of the exploratory analyses.

## **2. BACKGROUND**

Cardiogenic Shock complicating acute myocardial infarction (AMICS) is associated with significant mortality, with rates ranging from 40-60% (Kolte et al.; Wayangankar et al., 2016). To date, only early mechanical reperfusion has been shown to have a significant impact on mortality (Hochman et al., 2001). Hemodynamic support is commonly employed in patients with more severe forms of shock, but there remains considerable debate regarding the need, type of device, and timing of deployment. Moreover, approaches in the United States and Europe differ widely (Thiele et al., 2015; O'Neill et al., 2017), and randomized trials have yielded results that have failed to clarify the optimal strategies, resulting in broad clinical variation in treatment with both cost and outcome implications.

In addition to prompt mechanical reperfusion, the most commonly utilized adjunctive hemodynamic support include intra-aortic balloon counterpulsation (IABP), the micro-axial Impella 2.5, CP, and 5.0 systems, and extracorporeal membrane oxygenation (ECMO). Intra-aortic balloon counter-pulsation remains the most widely used device, although the hemodynamic effects are quite modest, with limited improvement in cardiac output despite diastolic augmentation and afterload reduction (Kern & Sato, 2016). In the IABP Shock II trial, 600 patients were randomized in open label fashion to IABP vs. no IABP in addition to mechanical reperfusion. A majority of patients received IABP after reperfusion, and there was no impact on mortality at 30 days or one year (Thiele et al., 2012). Based on the results of this trial, the European guidelines have been updated with a Class III recommendation for IABP in cardiogenic shock with the US with a Class IIb recommendation (ESC/EACTS, 2014; Levine et al., 2016).

Impella is a trans-catheter axial flow pump that can be delivered percutaneously and can provide 2.5-5.0 L/min of forward flow depending upon the device used. While the use of Impella improves the degree of hemodynamic support compared to IABP (Seyfarth et al., 2008), in the open label randomized IMPRESS trial in 48 patients, short term mechanical circulatory support with Impella did not improve mortality compared to IABP, and was associated with multiple complications (Ouweneel et al., 2017). However, 92% percent of the patients presented with cardiac arrest and all required mechanical ventilation. In contrast, the USpella registry suggested that early initiation of hemodynamic support prior to PCI with Impella is associated with more complete revascularization and improved survival in the setting of refractory cardiogenic shock complicating acute myocardial infarction (O'Neill et al., 2014). Moreover, five Detroit area centers performed a pilot feasibility analysis to determine whether early routine use of mechanical circulatory support with Impella utilized before PCI is possible, and whether impact on outcomes could be tracked. Based on the early encouraging results, an algorithm with early MCS with Impella prior to PCI utilizing a structured de-escalation protocol has been launched as a national initiative (National Cardiogenic Shock Initiative).

Current clinical standards do allow for the delay of Impella implantation or based on the device materials or FDA approval or IDE marketing application/approval Impella is specifically for those with severe shock which outweighs the procedural risks and financial burden.

### **3. RATIONALE**

Existing protocols in Europe and the United States vary widely based upon device selection and timing of support, a finding that is complicated by the limited data in a condition that is difficult to evaluate (Thiele et al., 2015; O'Neill et al., 2014; Diepen et al., 2017). Protocols in Europe suggest the deployment of MCS following revascularization, an approach which may underutilize a key pathway to better outcomes (O'Neill et al., 2014; Zeymar & Thiele, 2017; Brodie et al., 1999). In contrast, a significant concern for the National Cardiogenic Shock Protocol is that the existing

protocol may lead to Impella utilization in milder forms of shock when it may not be needed, resulting in potentially high artificial survival rates, unnecessarily expensive resource utilization, and life-threatening complications. Moreover, alternative devices, such as IABP or ECMO, may be more appropriate in specific clinical situations (small femoral anatomy, mitral regurgitation, RV failure, hypoxemia).

A recent American Heart Association Scientific Statement on the contemporary management of Cardiogenic Shock advocates for the development of regionalized systems of care and outlines future research priorities (Diepen et al., 2017). The statement notes that when, how, and which MCS device should be used remains unclear. Thus, outcomes of treatment in specialized cardiogenic shock centers which offer all treatment options, should be evaluated further.

The objective of the Carolinas Cardiogenic Shock Initiative will be to evaluate outcomes associated with utilization of MCS prior to PCI or delayed implementation in patients after reperfusion, based upon shock severity. An algorithm will be utilized which allows device variation based upon patient specific factors, employing a protocol driven approach to de-escalation in specialized shock centers with access to a variety of treatment options. Whether this can improve upon the protocol adopted by the National Cardiogenic Shock Initiative is unknown. However, the initiative addresses specific concerns that have arisen, leading to broad variation in the international approach to cardiogenic shock. A likely secondary benefit, is that a regionalized protocol should reduce center specific provider variation, allowing better outcome analysis and ability to execute specific protocol adjustments as a quality improvement initiative.

Previous research suggests that one of the only interventions to show a benefit to patient outcomes in adults who present with AMICS, is early mechanical reperfusion, with Impella being one of the more commonly used devices for treatment. However, variation exists across sites and facilities in patient survival rates and other clinical outcomes. Mechanical intervention also comes with its own risk. Implantation of Impella is an invasive and possibly risky procedure, with several possible side effects. There is also the possibility of the patient's financial burden from the admission and procedure.

Previous work has been done to identify key treatment elements which could be built into a widely accepted and utilized treatment algorithm for individuals who present with AMICS. However, further evaluation of comparing patient outcomes and treatment plans based on multiple aspects of the diagnosis, is needed to provide informed advice and guidance to patients. This project seeks to examine further diagnosis detail to determine if timed or delayed mechanical intervention is appropriate for patients with AMICS, based on shock severity.

